10.2.1.4 Adverse Events by "Reasonably Possibly Related" Relationship

TEAEs will also be summarized by MedDRA SOC and MedDRA PT, assessed with a Reasonable Possibility of being related to study drug by the Investigator. If a subject has an AE with an unknown relationship, then the subject will be counted in as 'related.'

10.2.1.5 Adverse Events by Preferred Term in Decreasing Frequency

TEAEs will be summarized for each treatment group by MedDRA PT in decreasing frequency of all risankizumab group.

10.2.1.6 Areas of Safety Interest

The Areas of Safety Interest (ASI) categories are listed in Appendix [12.7](#). These will be summarized and presented using primary MedDRA query and MedDRA PT.

Additional ASIs may be considered for tabulation/summary based on recommendations from Clinical and Safety teams, as deemed appropriate.

10.2.1.7 Adverse Events by 100 Patient Years

TEAEs will be summarized by event rate per 100 patient years, defined as

$$100 \times \frac{\text{Number of TEAEs}}{\text{Total Patient Years}}$$

where total patient years is defined as below.

- Total patient years of SC period is defined as (min (the last risankizumab SC dose date in Study M15-989 + 140 days, the first dose date of risankizumab in Study M16-000 sub-Study 3) - the first dose date of risankizumab SC in Study M15-989)/365.25.
- Total patient years of IV period is defined as (min (the last risankizumab IV dose date + 140 days, the first dose date of risankizumab SC) - the first dose date of risankizumab IV in Study M15-989)/365.25.
- Total patient years of "all risankizumab" is defined as (min (the last risankizumab dose date in Study M15-989 + 140 days, the first dose date of risankizumab in Study M16-000 sub-Study 3) - the first dose date of risankizumab in Study M15-989)/365.25.

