1. Visit 1 of this LT extension study should preferably be performed in one visit combined with the last visit of the preceding trial 1311.6 or during the interim period of maximum 5 days after completion of the last visit in 1311.6. If an EoT colonoscopy has not been performed during E1 within 1311.6, it must be performed between V1 and V2 in 1311.20/M15-989.
2. Assessments performed at the last visit in the previous trial do not have to be repeated at visit 1 in this trial. Assessments scheduled but not performed at the last visit in the previous trial should be repeated at Visit 1 in this trial, and the results entered into the CRFs of both trials 1311.6 and 1311.20/M15-989.
3. For patients who discontinue study medication before scheduled EoT visit, an early EoT visit should be performed. After last dose of study medication, a 140 day follow-up call should be scheduled. Upon EC/CA approvals of Study M16-000 protocol amendment 4, patients receiving treatment in M15-989 will have the option to enroll into M16-000 Sub-Study 3 after completing the EoT visit.
4. Must be performed at Visit 1 and starting from Visit 2 prior to each study drug administration in females of childbearing potential. In case of positive result, serum pregnancy test will be performed. Study drug will only be administered if pregnancy is ruled out.
5. Positive QuantiFERON-TB Gold In-Tube tests need not to be repeated. If TB or infection is suspected at any time during the study, a routine work up including chest x-ray and a QuantiFERON-TB Gold In-Tube test or an infection assessment must be performed at investigator's discretion and according to local guidelines.
6. Assessment of AE after subcutaneous injections will also include assessment of local tolerability. The assessment of local tolerability should be done just before the patient leaves the investigator site.
7. All assessments are to be completed prior to study drug administration, unless otherwise specified.
8. An end of trial call should be performed for both patients that agree to enroll into M16-000 Sub-Study 3 OLE or those that do not choose to participate.
9. For details of laboratory tests see [Section 5.2.3](#), [Table 5.2.3:1](#) and [Table 5.2.3:2](#).

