3.3.4 Removal of patients from therapy or assessments

3.3.4.1 Removal of individual patients

An excessive rate of withdrawals may render the study results uninterpretable; therefore unnecessary withdrawal of patients must be avoided. Patients who discontinue their treatment early should undergo all study required procedures including an early EoT visit and colonoscopy, as defined in [Section 6.](#)

Patients have the right to withdraw from the study at any time without the need to justify the decision.

The sponsor reserves the right to terminate a patient from the trial for non-compliance.

The investigator has the right to remove patients from the study for non-compliance.

Furthermore, patients' treatment must be discontinued early due to lack of efficacy (defined as an endoscopically confirmed CDAI re-increase to >100 points above baseline in 1311.6 and a CDEIS >4), or for other reasons (as described below). If, in the investigator's opinion, such a patient requires alternative medical therapy for their Crohn's disease, the study treatment must be stopped and patients may receive conventional treatment for active disease as per investigator's judgment.

Criteria and rules for stopping patient treatment due to reasons other than lack of efficacy include:

- Development of a toxicity or adverse event which warrants drug discontinuation.
- Development of any potentially life-threatening toxicity.
- Any concomitant illness that prevents compliance.
- The patient is unwilling to continue in the trial.

- Pregnancy in a female participant.
- Patient lost to follow-up despite reasonable efforts to make contact with the patient.
- Patient is no longer able to participate for other medical reasons (e.g., surgery, adverse events or other diseases).
- The DMC may recommend termination or re-design of the trial for other relevant issues of safety.

Patients who discontinue from the study after Visit 2 will be considered as "early discontinuations" and the reason for premature discontinuation must be recorded in the eCRFs. The data will be included in the trial database and will be reported.

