5.2.2.2 Adverse event and serious adverse event reporting

AE Collection

The Investigator shall maintain and keep detailed records of all AEs in their patient files.

The following must be collected and documented on the appropriate CRF(s) / eCRF by the Investigator:

- From signing the informed consent onwards through the Residual Effect Period (REP), until individual patient's end of trial: all AEs (serious and non-serious) and all AESIs.

The residual effect period (REP) for BI 655066/ABBV-066 (risankizumab) is defined as 20 weeks after the last trial medication application. Therefore, all AEs which occurred through the treatment phase and throughout the REP will be considered as on treatment (see [Section 7.3.3](#)). Events which occurred after the REP will be considered as post treatment events.

AE reporting to sponsor and timelines

In the event of an SAE, whether associated with study drug or not, the Investigator will notify Clinical Pharmacovigilance within 24 hours the site being made aware of the SAE by entering the SAE data into the electronic data capture (EDC) system. SAEs that occur prior to the site having access to the RAVE system, or if RAVE is not operable, should be documented on the SAE Non-CRF forms and emailed (preferable route) or faxed to Clinical Pharmacovigilance within 24 hours of the site being made aware of the SAE.

Email: [contact]
FAX to: [contact]

Risankizumab
1311.20/M15-989 Protocol Amendment 4
EudraCT 2015-001834-15

For safety concerns, contact the Immunology Safety Team at:

[figure not shown]
Immunology Safety Team

[name]
[name]

For any subject safety concerns, please contact the physician listed below:

Primary Therapeutic Area Medical Director:

In emergency situations involving study subjects when the primary Therapeutic Area Medical Director is not available by phone, please contact the 24-hour AbbVie Medical Escalation Hotline where your call will be re-directed to a designated backup AbbVie Therapeutic Area Medical Director:

Phone: 

AbbVie will be responsible for Suspected Unexpected Serious Adverse Reactions (SUSAR) reporting for the Investigational Medicinal Product (IMP) in accordance with global and local guidelines and Appendix A of the Investigator Brochure which will serve as the Reference Safety Information (RSI). The RSI in effect at the start of a DSUR reporting period serves as the RSI during the reporting period. For follow up reports, the

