10.2.3 Listing of Adverse Events

The following summaries of AEs will be prepared.

- Listing of Subjects with Treatment-Emergent Adverse Events of Special Interest
- Listing of Subjects with Treatment-Emergent Serious Adverse Events
- Listing of all adverse events that led to discontinuation of study drug.
- Listing of all deaths.

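### Patient-years in SAP 10.2.1.7 do not stop at death or at the end of AE observation, so the rates per 100 patient-years are too low if patients leave before last dose + 140 days

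*SAP*

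**What the plan says.** SAP 10.2.1.7 defines the rate as 100 times the number of TEAEs divided by total patient-years, and defines patient-years three times.

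- All risankizumab: from first dose to "min (the last risankizumab dose date in Study M15-989 + 140 days, the first dose date of risankizumab in Study M16-000 sub-Study 3").
- SC period: from first SC dose to "min (the last risankizumab SC dose date in Study M15-989 + 140 days", or to the first M16-000 dose if that is earlier.
- IV period: from first IV dose to "min (the last risankizumab IV dose date + 140 days, the first dose date of risankizumab SC").

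The other time rules in the SAP add no stop at death or last contact. This was checked in 6.2 (final observation), the window footnotes in 6.4, 8.2.1 (exposure) and 10.2.1 (TEAE window).

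The documents foresee patients leaving observation early. Protocol 3.3.4.1 states: "Patients have the right to withdraw from the study at any time without the need to justify the decision". It also gives as a reason for stopping treatment: "Patient lost to follow-up despite reasonable efforts to make contact with the patient". SAP 8.1 tabulates loss to follow-up, and SAP 10.2.3 plans a "Listing of all deaths".

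Stopping study drug does not by itself end observation. Footnote 3 of the flow charts requires an early EoT visit and adds: "After last dose of study medication, a 140 day follow-up call should be scheduled". Under Protocol 5.2.2.2, where the residual effect period (REP) is 20 weeks, "all AEs which occurred through the treatment phase and throughout the REP will be considered as on treatment".

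**The concern.** A rate per unit of time needs a denominator that contains only time in which an event could have been recorded. A patient who has died, withdrawn from the study or been lost can add nothing to the TEAE count, yet the formulas still credit days up to last dose + 140. The count stays the same and the denominator grows, so the error can only lower the rate.

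Long-term safety is the primary objective (Protocol 2.2, SAP 4.1), and this rate is the SAP's AE summary that adjusts for unequal follow-up. Unequal follow-up is expected: the Amendment 4 rationale says that treatment durations will differ between patients. Too low a rate is the unfavourable direction for a safety summary.

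**Working it through.** The documents state no patient-year total and no AE rate, so there is no planned figure to reproduce. The check asks how far the rate moves under stated assumptions.

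**Inputs from the documents**
- N = 60 planned patients (Protocol 3.1).
- Credit after last dose: 140 days; days per year: 365.25 (SAP 10.2.1.7).
- Full planned SC dosing: week 4 to 204, 6 to 206 or 16 to 216 (Flow Charts 1 to 3). Each is 200 weeks, so D = 1400 days from first to last dose.
- D = 868 days is a shorter case: 924 - 56, from the last bounded exposure interval and the 56-day extension in SAP 8.2.1.
- IV infusions at weeks 4, 8 and 12, and first SC dose at week 16 (SAP Flow Chart 3). First to last infusion is 56 days, and first infusion to first SC dose is 84 days.

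**Assumptions (not in the documents)**
- Share affected, p: 5% to 20%, that is 3 to 12 of 60.
- Unobserved days credited per affected patient, L: 140 if there is no contact after the last dose; 84 if last observed 56 days after it (140 - 56).
- D = 364 days as a short-dosing case.
- IV group of 10 or 5 patients.

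**Per affected patient.** 140/365.25 = 0.38 patient-years; 84/365.25 = 0.23 patient-years.

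**SC and all-risankizumab rates.** The TEAE count is unchanged, so the understatement is unobserved time divided by credited time. Two versions bracket the unaffected patients:
- (a) everyone is credited D + 140: p × L / (D + 140);
- (b) unaffected patients roll over 56 days after last dose: p × L / [p(D + 140) + (1 - p)(D + 56)].

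At D = 1400, credited time is 60 × 1540/365.25 = 253.0 patient-years if everyone is credited 140 days, and 60 × 1456/365.25 = 239.2 if everyone rolls over at 56 days. Over-credit runs from 3 × 84/365.25 = 0.69 to 12 × 140/365.25 = 4.60 patient-years.

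| D (days) | p = 5%, L = 84: (a) / (b) | p = 20%, L = 140: (a) / (b) |
|---|---|---|
| 1400 | 4.2/1540 = 0.27% / 4.2/1460.2 = 0.29% | 28/1540 = 1.82% / 28/1472.8 = 1.90% |
| 868 | 4.2/1008 = 0.42% / 4.2/928.2 = 0.45% | 28/1008 = 2.78% / 28/940.8 = 2.98% |
| 364 | 4.2/504 = 0.83% / 4.2/424.2 = 0.99% | 28/504 = 5.56% / 28/436.8 = 6.41% |

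One affected patient of 60 at D = 1400 gives 84/92400 = 0.09% up to 140/87444 = 0.16%, where 87444 = 1540 + 59 × 1456.

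For Flow Chart 3 patients, all-risankizumab time starts 84 days earlier, which makes the overall percentages slightly smaller.

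**IV-period rate.** A patient with three infusions who is lost at day 84 without starting SC is credited 56 + 140 = 196 days. With the other IV patients at 84 days each:
- 10 patients: observed 840 days, credited 9 × 84 + 196 = 952; 840/952 = 0.882, so the rate is about 12% too low.
- 5 patients: observed 420 days, credited 4 × 84 + 196 = 532; 420/532 = 0.789, so the rate is about 21% too low.

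**The case against.** The strongest reply is that the 140-day limit is a deliberate convention. For patients who do not roll over it matches the TEAE window in SAP 10.2.1 and the 20-week residual effect period in Protocol 5.2.2.2 and 7.3.3, so numerator and denominator share one nominal window. With the early EoT visit and the 140-day call, most patients should be observed to its end. Nothing shows that any patient is affected. The upper figures need 12 of 60 patients with no contact at all after the last dose. No hypothesis is tested.

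Most of this stands, and it sets the severity. It does not remove the gap: a shared nominal window is right only for patients observed throughout it, and the plan itself expects some who will not be.

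Three stronger readings are tempting, and the documents do not support them.
- A reader might infer that every early discontinuation inflates the denominator. A patient who stops drug but is followed to the 140-day call contributes observed time, and AEs in that time count.
- A reader might infer that the AE percentages are biased too. The incidence tables count patients and do not use patient-years.
- A reader might take the 12% and 21% as estimates for this trial. The IV group sizes are assumed, and patients who fail re-induction are also due an EoT visit and, unless they enrol in M16-000, a 140-day call (Protocol 3.1).

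**Conclusion.** The concern holds as a low-severity point. As written, all three definitions credit unobserved time to any patient who does not start the next treatment and leaves observation before last dose + 140 days. The direction is certain; the size is not, because the number of such patients is not in the documents.

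For the SC and all-risankizumab rates the effect is minor under the assumptions shown, although it grows as dosing gets shorter. Those percentages must not be read as covering the IV-period rate. There the observed time per patient is short, and a single lost patient could shift the rate noticeably. The effect is zero for patients followed to the 140-day call or dosed in M16-000 within 140 days. What is at stake is the accuracy of one descriptive safety summary.

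**What to change.** In all three formulas of SAP 10.2.1.7, end person-time at the earliest of:
- last dose + 140 days;
- first M16-000 dose (for the IV period, first SC dose);
- date of death;
- date of end of study participation or last study contact;
- the data cut-off date, if the rate is used in an interim analysis (SAP 4.5).

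State that stopping study drug alone does not end person-time, so that time and AEs in the 20-week residual effect period still count while the patient is followed. The SAP should also name the recorded date that serves as end of participation or last contact, since none of its time rules uses one.

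The cost is SAP wording and one derived date per patient and period. Reported rates would be slightly higher where patients are affected and unchanged otherwise. Visits and the timing of the analysis stay as they are.

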10.2.2 SAEs (Including Deaths) and Adverse Events Leading to Study Drug Discontinuation

The number and percentage of subjects experiencing treatment-emergent SAEs and adverse events leading to discontinuation of study drug will be tabulated according to the primary MedDRA SOC and PT for each treatment group.

10.2.3 Listing of Adverse Events

The following summaries of AEs will be prepared.

- Listing of Subjects with Treatment-Emergent Adverse Events of Special Interest
- Listing of Subjects with Treatment-Emergent Serious Adverse Events
- Listing of all adverse events that led to discontinuation of study drug.
- Listing of all deaths.

10.3 Analysis of Laboratory Data

Data collected from the central and local laboratories, including additional laboratory testing due to an SAE, will be used in all analyses.

Hematology parameters: White Blood Cell (WBC) count, Neutrophils, Lymphocytes, Red Blood Cell (RBC) count, Hematocrit, Hemoglobin, Platelets count.

Chemistry parameters: Total Bilirubin (TBL), Direct Bilirubin, Gamma Glutamyl Transferase (GGT), Alkaline Phosphatase (ALP), Serum glutamic oxaloacetic transaminase (SGOT)/Aspartate Aminotransferase (AST), Serum glutamic pyruvic transaminase (SGPT)/Alanine aminotransferase (ALT), Total Protein, Albumin, Glucose, Creatinine, Potassium, Sodium, Calcium, Creatine Phosphokinase (CPK), Cholesterol, LDL cholesterol, HDL cholesterol, Triglycerides.

Urinalysis parameters: PH value.

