5.2 SAFETY

5.2.1 Endpoint(s) of safety

There is no primary endpoint in a statistical sense in this study (see [Section 7.2](#)). Instead, safety and tolerability will be assessed in a descriptive way based on:

- Physical examination
- Vital signs (blood pressure (BP), heart rate (HR) and oral body temperature)
- 12-lead ECG (electrocardiogram)
- Clinical laboratory tests (haematology, clinical chemistry and urinalysis)
- Adverse events
- Immunogenicity

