5.2.3 Assessment of safety laboratory parameters

The laboratory tests will be performed as listed in [Table 5.2.3: 1](#) and [Table 5.2.3: 2](#). Instructions on sample collection, sample handling/ processing, and sample shipping will be provided to the investigator site file by the central laboratory. For time points of laboratory sampling, see [Flow chart 1](#), [Flow chart 2](#) and [Flow chart 3](#).

Laboratory results of the patients will be available in real time to the respective investigator and to the clinical monitor of each country (central laboratory website), and selected abnormal laboratory alerts will be sent automatically to the sites and to the sponsor in real time. PK, PD and biomarker data will not be available to the investigators or local clinical monitors but the Trial Team (sponsor) in a blinded manner and when relevant, in an unblinded manner to the DMC. Laboratory results will be reported as the absolute value of the measurement obtained on a study patient.

Clinically relevant laboratory values will be commented on in the eCRF. A clinically relevant value may be either in- or outside the reference range. Clinically relevant abnormal laboratory test results must be repeated using an unscheduled visit lab kit and must be repeated until normalisation or stabilisation or until an alternative explanation has been found. Clinically relevant abnormal laboratory values will be also graded for intensity by using RCTC Version 2.0 criteria.

Table 5.2.3: 1 Laboratory tests

Category	Test name
Hæmatology	Hematocrit (Hct) Hemoglobin (Hb) Red Blood Cell Count / Erythrocytes Reticulocyte Count White Blood Cells / Leucocytes Platelet Count
Differential automatic (relative and absolute count)	Neutrophils Eosinophils Basophils Monocytes Lymphocytes
Differential manual (relative and absolute count) (if differential automatic is abnormal)	Neutrophils, Bands Neutrophils, Polymorphonuclear (PMN) Eosinophils Basophils Monocytes Lymphocytes
Coagulation	Partial Thromboplastin Time (PTT) Prothrombin Time (Quick / INR) Fibrinogen
Enzymes	AST/GOT, SGOT ALT/GPT, SGPT Alkaline Phosphatase (AP/ALP) Creatine Kinase (CK) CK-MB if CK is elevated Gamma-Glutamyl Transferase (GGT/γ-GT) Lactic Dehydrogenase (LDH) Lipase Amylase
Specific gamma-globulin quantification	IgE [†] , IgG

only in case of allergic reaction

Table 5.2.3: 1 Laboratory tests (con't)

Category	Test name

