Substrates	Glucose Creatinine and Creatinine Clearance Blood urea nitrogen Bilirubin Total Bilirubin Direct Protein, Total Albumin hsC-Reactive Protein Uric Acid Cholesterol, Total High density lipoprotein (HDL) Cholesterol Calculated Low Density Lipoprotein (LDL) Cholesterol Triglycerides
Electrolytes	Calcium Sodium Potassium Chloride Bicarbonate
Hormones	Thyroid stimulating hormone (screening visit only) Free T3, Free T4 if TSH <LLN or >ULN
Urinalysis (Stix)	Urine Nitrite Urine Protein Urine Glucose Urine Ketone Urobilinogen Urine Bilirubin Urine RBC/Erythrocyte Urine WBC/Leukocytes Urine pH
Urine sediment (microscopic examination) (if urine analysis abnormal)	Urine Sediment Bacteria Urine Casts in Sediment Urine Squamous Epithelial Cells Urine Sediment Crystals, Unspecified Urine Sediment RBC/Erythrocytes Urine Sediment WBC/Leucocytes

Table 5.2.3: 2 Other sampling and testing

Autoantibodies	Human Anti-BI 655066/ABBV-066 (risankizumab) Antibodies (ADA)
Serum Sample for Biomarkers	Refer to Section 5.6
Fecal sample	Calprotectin

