7.3.3 Safety analyses

Since the main objective of this study is long term safety, the primary focus would be on incidence of drug-related AE and serious infection.

Adverse events will be coded using the Medical Dictionary for Regulatory Activities (MedDRA) coding dictionary. Summary tables and listings will be produced. All adverse events with an onset between start of treatment and end of the residual effect period (REP), a period of 20 weeks after the last dose of trial medication, will be assigned to the treatment period for evaluation.

All treated patients will be included in the safety analysis.

Statistical analysis and reporting of adverse events will concentrate on treatment-emergent adverse events. To this end, all adverse events occurring between start of treatment and end of the residual effect period will be considered 'treatment-emergent'. Adverse events that start before first drug intake and deteriorate under treatment will also be considered as 'treatment-emergent'. Frequency, severity, and causal relationship of adverse events will be tabulated by system organ class and preferred term after coding according to the current version of the Medical Dictionary for Drug Regulatory Activities (MedDRA). Safety analyses will focus on adverse events related to early discontinuation, immune suppression and injection site effects.

Laboratory data will be analysed both quantitatively as well as qualitatively. The latter will be done via comparison of laboratory data to their reference ranges. Values outside the reference range as well as values defined as clinically relevant will be highlighted in the listings. Treatment groups will be compared descriptively with regard to distribution parameters as well as with regard to frequency and percentage of patients with abnormal values or clinically relevant abnormal values. Analysis of laboratory measures will focus on haemotologic measures of immune suppression.

Vital signs, physical examinations, or other safety-relevant data observed at screening, baseline, during the course of the trial and at the end-of-trial evaluation will be assessed with regard to possible changes compared to findings before start of treatment.

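### SAP 10.3 gives no specified output for 19 of 45 routine safety laboratory tests, and for no test does it give the out-of-range listing that protocol 7.3.3 promises

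*SAP*

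**What the plan says.** Protocol 5.2.1 bases the descriptive safety assessment partly on "Clinical laboratory tests (haematology, clinical chemistry and urinalysis"). Protocol 7.3.3 then commits to two qualitative outputs for laboratory data. The first is a listing: "Values outside the reference range as well as values defined as clinically relevant will be highlighted in the listings". The second is a summary of the "frequency and percentage of patients with abnormal values or clinically relevant abnormal values". The same section adds an emphasis: "Analysis of laboratory measures will focus on haemotologic measures of immune suppression". None of these sentences is limited to a subset of tests.

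Protocol Table 5.2.3:1 sets out what is collected. Its urine dipstick (Stix) entry reads "Urine Nitrite Urine Protein Urine Glucose Urine Ketone Urobilinogen Urine Bilirubin Urine RBC/Erythrocyte Urine WBC/Leukocytes Urine pH", which is nine results.

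SAP 10.3 lists the parameters by name: 7 haematology, 18 chemistry and, for urine, "Urinalysis parameters: PH value". SAP 10.3.1 gives counts and listings for liver thresholds and listings of potential Hy's Law cases. SAP 10.3.2 gives change from baseline, low/normal/high shift tables from baseline to the last value in each treatment period, and a listing of patients reaching CTC Grade 3 or higher on selected variables. SAP 11 says that the sponsor's analysis conventions apply. It does not mention a reduced set of laboratory tests.

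**The concern.** Long-term safety is the primary objective and the trial has no hypothesis test, so the specified tables and listings are the safety result. Two things are missing from them.

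First, a named safety class, urinalysis, is reduced to pH. Urine protein, blood, leukocytes and nitrite are collected but have no specified output. The same holds for some haematology and chemistry tests.

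Second, even for the named parameters the SAP does not deliver what protocol 7.3.3 describes. A shift table that uses only the last value in a period cannot count a patient whose result was abnormal earlier and then recovered. In a study of about four years, such transient changes are part of what a long-term safety summary should show.

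**Working it through.** The plan states no figure to reproduce. The check is a count of SAP 10.3 against protocol Table 5.2.3:1, followed by a comparison of outputs.

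**Step 1: coverage.** The count takes unconditional tests in the three classes of protocol 5.2.1. It leaves out tests done only on a trigger (manual differential, CK-MB, IgE, free T3/T4, urine sediment) and also coagulation, IgG, hs-CRP and TSH (see the objection). Creatinine and its clearance count once.

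| Group in Table 5.2.3:1 | In table | In SAP 10.3 | Not in SAP 10.3 |
|---|---|---|---|
| Haematology | 6 | 5 | 1: reticulocytes |
| Automatic differential | 5 | 2 | 3: eosinophils, basophils, monocytes |
| Enzymes | 8 | 5 | 3: LDH, lipase, amylase |
| Substrates (without hs-CRP) | 12 | 10 | 2: blood urea nitrogen, uric acid |
| Electrolytes | 5 | 3 | 2: chloride, bicarbonate |
| Urine Stix | 9 | 1 | 8: all except pH |
| Total | 45 | 26 | 19 |

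- SAP total: 7 + 18 + 1 = 26, and all 26 appear in the protocol table.
- Unlisted: 45 − 26 = 19, and 19/45 = 42%.
- By class: haematology 1 + 3 = 4; chemistry 3 + 2 + 2 = 7; urine 8.

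**Step 2: listings.** The SAP specifies three kinds of laboratory listing: liver thresholds, Hy's Law combinations, and CTC Grade 3 or higher. The last covers the 14 chemistry variables of SAP Table 8 and the 5 haematology variables of SAP Table 9. That leaves 26 − 14 − 5 = 7 named parameters with no threshold for any listing: RBC, haematocrit, direct bilirubin, total protein, LDL, HDL and urine pH. For the others the threshold is severe abnormality or a liver multiple, not the reference range. The reference-range listing of protocol 7.3.3 is therefore absent for the 26 as well as for the 19.

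**Step 3: frequencies.** Outside the liver criteria, the only counts based on abnormality are the baseline-to-final shifts. Take a patient with neutrophils of 1.2 × 10⁹/L at one mid-study visit, normal at baseline and at the last visit. By SAP 12.8 this is Grade 2, so it does not enter the Grade 3 listing. The shift table records normal to normal. The value contributes to a visit mean and to no count, although neutrophils belong to the protocol's stated focus.

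**Step 4: how much urine data is involved.** In Flow Charts 1 and 2 the first dose is at Visit 2, after that visit's assessments. Post-dose urinalysis is therefore scheduled at Visits 3 to 27 (25 visits) plus the end-of-trial visit: 25 + 1 = 26 at most, and fewer for patients who stop earlier.

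**The case against.** The strongest reply has four parts.

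- **Choosing parameters is the SAP's job.** Protocol 7.3.3 gives no test list, and its frequency clause sits in a sentence about comparing treatment groups, which looks like template text in a single-group trial. The protocol also sets a focus, and WBC, neutrophils and lymphocytes meet it. This partly stands: a reasoned selection would be acceptable. But a focus excludes nothing, urinalysis is named in 5.2.1, and the SAP gives no reason for keeping only pH.
- **Adverse events cover what matters.** Results judged clinically relevant are recorded as adverse events and tabulated by term and severity. The protocol adds: "Clinically relevant abnormal laboratory values will be also graded for intensity by using RCTC Version 2.0 criteria". The frequency clause offers abnormal or clinically relevant values as alternatives, so adverse event tables deliver much of the second. This stands as mitigation. It does not supply the listing, which protocol 7.3.3 promises for out-of-range values and clinically relevant values alike, and adverse event recording depends largely on investigator judgement.
- **The shift-table wording could be read broadly.** SAP 10.3.2 refers to each parameter of the three classes. But SAP 10.3 has just named those parameters, so a programmer would use that list.
- **Data listings are mentioned in SAP 6.2.** That remark concerns data beyond 140 days after the last dose. It specifies no laboratory listing.

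A reader might infer more than the documents support, in three ways:

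- One might raise the count of unlisted tests by adding coagulation ("Partial Thromboplastin Time (PTT) Prothrombin Time (Quick / INR) Fibrinogen"), IgG, hs-CRP and TSH. Coagulation and IgG are separate categories in Table 5.2.3:1, and the flow-chart laboratory row does not name them, so how often they were sampled is not stated. The SAP summarises hs-CRP as an efficacy endpoint. TSH is taken at screening only, so it has no on-treatment frequency.
- One might think that the 26 named parameters are fully covered. Steps 2 and 3 show that they are not.
- One might conclude that a serious urine or blood abnormality would go unseen. The adverse event route and the data monitoring committee's review of laboratory data argue against that.

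**Conclusion.** The point holds as a minor one. Nineteen of 45 unconditional tests in the protocol's three laboratory classes have no specified output, and urinalysis is left essentially unanalysed. Separately, for every test the out-of-range listing is missing, and outside the liver criteria abnormal-value counts rest on final values only.

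The size depends on the counting rules in the working and on reading SAP 10.3 as a closed list. The tests are not equally important: basophils and urobilinogen matter less than urine protein or eosinophils, so 42% measures coverage, not lost safety information. The main immune cell counts, liver tests and infection searches are specified, and no inference or decision rule changes. What is at stake is whether the report delivers the descriptive laboratory analysis that the protocol describes.

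**What to change.** Amend SAP 10.3.2 in three places.

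1. Add a listing that flags values outside the reference range for all collected safety laboratory tests, named in SAP 10.3 or not. This also takes in coagulation and IgG wherever they were sampled.
2. Add the number and percentage of patients with any treatment-emergent abnormal result, using the same window as for adverse events. Report urine protein, blood, leukocytes and nitrite as negative/positive. For haematology and chemistry, count any value outside the reference range, and add eosinophils and monocytes to the parameters.
3. Keep shift and change tables only where a feeder-study baseline exists. SAP 6.1 takes the safety baseline from that study, and the documents do not show that the added tests were measured there. The counts in item 2 can be made without one.

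If the sponsor prefers to leave some tests out of the tables, SAP 11 should say which and why.

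The cost is one categorical table, one listing and modest programming, with no new data collection. The downside is more output. Counts of patients ever outside the range also grow with the number of visits, so the tables should give the number of patients tested and be read as description.
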